6.6. Subject Withdrawal

Subjects will be withdrawn from drug administration if any of the following occur:

- Subject refuses to continue treatment.
- Severe ACS, as defined in the protocol (see [Section 7.2.4.2.1](#)).
- Acute stroke, or other acute central nervous system changes.
- Serious systemic infection (suggestive of sepsis) with fever $>39^{\circ}$ C (102.2° F).
- Serious systemic infection, evidenced by clinical signs and symptoms, and/or microbiological investigations, consistent with this diagnosis requiring escalation in medical care, such as meningitis, bacteremia, empyema, or osteomyelitis. Simple pneumonia, responding to antibiotics and not requiring intensive care unit (ICU) care or packed RBC transfusion, will not require withdrawal from study drug administration.
- Elevated WBC $>50,000/\text{mm}^3$.
- Unexpected rise in creatinine, or fall in eGFR, consistent with acute renal failure (see [Section 7.2.4.1](#)).

- Pregnancy.
- Severe cutaneous manifestation (see [Section 7.2.4.3.1](#)).

All randomized subjects who withdraw from drug administration during the double-blind study treatment period, but continue on the study (including subjects who are randomized but not treated), will continue to be followed as per the procedures outlined in the Schedule of Activities ([Table 1](#)), up to Day 35 Post-Discharge Follow-Up visit (Visit 4).

[REDACTED] All efforts will be made to obtain safety data and other endpoint data from subjects.

[REDACTED]

A subject may be withdrawn from the study for any of the safety concerns as listed above, in addition to the following reasons:

- Consent is withdrawn.
- Subject refuses procedures/observations.
- Other reasons (eg, significant protocol violations, non-compliance).

All abnormal laboratory events of clinical significance should be followed until the laboratory values have returned to normal or baseline levels.

If a subject has any clinically significant, study related abnormalities at the conclusion of the study, the Pfizer medical monitor (or designated representative) should be notified and every effort should be made to arrange follow-up evaluations at appropriate intervals to document the course of the abnormalities.

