9.2. Efficacy Analysis

Complete details (including censoring rules for the time-to-event endpoints) on the efficacy analyses are provided in the SAP. The statistical analysis methods will be used for the Primary Analysis Population with Cohort 1 and Cohort 2 combined. In addition, the same analyses will be conducted separately for the two cohorts. A gate-keeping approach will be used for analyses of Cohort 1 and Cohort 2 combined to control overall type I error for the primary and key secondary endpoints. Analyses for Cohort 1 and Cohort 2 combined would provide the basis for initial regulatory approval of rivipansel for the indication of treatment of VOC in SCD subjects.

The efficacy analysis will be performed for the full analysis set, an intent-to-treat (ITT) population which will include all randomized subjects in the study.

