9.2.1. Analysis of Primary Endpoint

The primary endpoint is time to readiness-for-discharge from the hospital. Time to readiness-for-discharge is defined as the difference between the readiness-for-discharge date and time (see [Section 7.1.1](#) for detail) and the start date and time of the first infusion of study drug in hours.

Below are examples of scenarios where subjects receive an infusion of study drug but do not meet the primary endpoint criteria:

- If one or more applicable criteria are not met for a subject before the subject is discharged or are missing, then the time to readiness-for-discharge will be treated as censored. If a subject dies in the hospital before all criteria are met, then the time to readiness-for-discharge will be treated as censored.
- If a subject is not hospitalized and prematurely terminates from the study before all criteria are met, the time to readiness-for-discharge will be treated as censored. If a subject is randomized but not infused with study drug, the time to readiness-for-discharge will be defined as the time from randomization to the time of the subject's termination and will be treated as censored.

Details on censoring rules for the time to readiness-for-discharge are provided in the SAP.

The primary analysis will be performed using the Cohort 1 and Cohort 2 populations combined, as well as Cohort 1 and Cohort 2 populations separately. The primary analysis to test the difference between the rivipansel and placebo groups will utilize a stratified log-rank test where the stratifications are age group (Cohort 1 and Cohort 2 combined or Cohort 1 only) and genotype. For Cohort 2, a log-rank test stratified by genotype will be performed.

A Cox regression model with age group (Cohort 1 and Cohort 2 combined or Cohort 1 only) and genotype as stratification variables will be used to estimate the treatment group hazard ratio and the corresponding two-sided 95% confidence interval. Median Time to readiness-for-discharge will be estimated using the Kaplan-Meier product limit method.

The number and percent of subjects who are documented to have achieved the event of readiness-for-discharge, as well as the number and percent of subject who were censored will be reported for each of the treatment groups.

Multiple sensitivity analyses will be conducted and will be fully described in the SAP.

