5. ANALYSIS SETS

5.1. Full Analysis Set

The primary analysis set for efficacy analyses is defined by the full analysis set (FAS) of subjects. The FAS will include all subjects who are randomized in the study.

5.2. 'PER PROTOCOL' Analysis Set

The primary endpoint will also be analyzed for the per-protocol analysis set (PPAS). The PPAS will be a subset of subjects from the FAS. Subjects who never received an infusion of study drug or had a protocol deviation or major violation that could affect efficacy will be excluded from the PPAS. The specific reasons for excluding subjects from the PPAS will be fully defined and documented before breaking the blind. The list of subjects along with the reasons for their exclusion from the PPAS will be stored in the Trial Master File (TMF).

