7. HANDLING OF MISSING VALUES

- Missing values for safety endpoints will not be imputed.
- For time to event and IV opioid use calculations, measurement begins from the start date and time of the first infusion (loading dose) of the study drug. If the start date and time of the first infusion of study drug (loading dose) are not available, including scenarios where the subject is randomized but not treated, the time of 12:00 (24-hr clock) on the randomization date, will be used (time of randomization is not collected as part of the study database).

- The time of discontinuation from study is not collected in the study database, therefore 23:59 (24-hr clock) on the date of discontinuation from study will be used, when the time of discontinuation from study is needed for the derivation of any endpoint.
- If the date of death is present, but the time of death is missing, 23:59 (24-hr clock) on the date of death will be used, when the time of death is needed in the derivation of any endpoint.

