For a treated subject, if any applicable criterion among C3-C6, has the latest start date and time for the last administration (of IV concomitant drug) present but the corresponding stop date and time missing due to discontinuation from the study, then that criterion is considered not met. In this case, the time corresponding to the unmet criterion, to be used in the computation of the censored TTRFD, will be 23:59 on the date of discontinuation from study.		
(v) Randomized and treated subjects with no data on C1-C6	Yes	TTRFD = 0 hours.
(vi) Randomized but not treated subjects [need to check if there is IV concomitant drug use based on eCRF data at or after 12:00 (24-hr clock) on the randomization date]	Yes	TTRFD = STOP—START; where
In the case of missing stop date/time in any of C3-C6 due to discontinuation from the study, the criterion is considered not met. The date/time of the unmet criterion will be 23:59 on the date of discontinuation from study.		STOP = Latest date and time among the dates and times for the met or unmet criteria from C3- C6 (data are not collected on C1 and C2 for untreated subjects);
For subjects who have no IV concomitant drug use based on eCRF data at or after 12:00 (24-hr clock) on the date of randomization, the criterion C3 is considered met at 12:00 (24-hr clock) on the date of randomization. Criteria C4-C6 are considered NA.		For subjects who have IV records at or after 12:00 (24-hr clock) on the date of randomization:
(vii) C3, C4, C5, C6: Latest stop date present, stop time missing	No	START = 12:00 (24-hr. clock) on the date of randomization
If the stop time is missing, but the corresponding stop date (for any IV concomitant drug administration) is available, the missing stop time will be imputed at 23:59 (24-hr clock), and this criterion will be considered met.		For subjects who have no IV records at or after 12:00 (24-hr clock) on the date of randomization:

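### Does the protocol's different censoring sentence for randomised-but-untreated subjects put the primary analysis at risk?

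*Protocol*

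**What the plan says.** Protocol 9.2.1 lists cases in which the primary endpoint is censored. The last reads "If a subject is randomized but not infused with study drug, the time to readiness-for-discharge will be defined as the time from randomization" to the subject's termination, treated as censored. The list is introduced by "Below are examples of scenarios where subjects receive an infusion of study drug but do not meet the primary endpoint criteria", which does not fit a subject who was never infused.

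SAP 7.1, Table 6(vi), also censors these subjects. Its start is "START = 12:00 (24-hr. clock) on the date of randomization". Its stop is the latest time among criteria C3 to C6 (IV opioids, IV hydration, IV antibiotics, transfusion). If a stop is missing because the subject left the study, "The date/time of the unmet criterion will be 23:59 on the date of discontinuation from study". If there is no IV record at or after noon, C3 counts as met at noon and C4 to C6 do not apply. Stop then equals start and the time is 0 h. The last cell of that row is broken in the text as read, so 0 h is inferred from the C3 rule; the parallel row of Table 8 states 0 h outright.

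SAP 7 gives the reason for noon: "time of randomization is not collected as part of the study database". SAP 5.1 keeps these subjects in the primary analysis: "The FAS will include all subjects who are randomized in the study". On precedence, Protocol 9.2 says "Complete details (including censoring rules for the time-to-event endpoints) on the efficacy analyses are provided in the SAP", and Protocol 7.1.1 and 9.2.1 repeat the referral for this endpoint.

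**The concern.** Two written rules cover the same subjects in the primary log-rank test, and the protocol's rule cannot be computed exactly because the clock time of randomisation is not in the database. Its end point, termination, is not defined there either.

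The possible effect is not trivial. Protocol 6.6 says that subjects who stop study drug but stay on study ("including subjects who are randomized but not treated), will continue to be followed as per the procedures outlined in the Schedule of Activities") are followed to the Day 35 post-discharge visit. If that visit were taken as termination, an untreated subject would remain in the risk set for about 35 × 24 = 840 h after discharge with no possibility of an event. The event count would not expose this: with 3 to 15 untreated of 300 and every treated subject reaching the event, 297 to 285 events remain, above the 282 required. Section 9 of the protocol also says that major changes to endpoint definitions or analyses will be carried into an amendment, which could be taken to mean that the protocol sentence still binds.

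**Working it through.** **1. Which rule governs.** The opening of Protocol section 9 lets the SAP modify what the protocol outlines and reserves an amendment for major modifications. Protocol 7.1.1, 9.2 and 9.2.1 each send the censoring rules to the SAP, and the 9.2.1 items are offered as examples. Both rules censor the untreated subject, so the event definition, the test and the event target are the same under either. A censoring time for this small group is the kind of detail the protocol delegates. Table 6(vi) governs.

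**2. Start time.** Noon on the randomisation date is an imputation of the protocol's starting point, not a rival to it. It can be wrong by at most about 12 h either way.

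**3. Stop time.**

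| Untreated subject | Protocol 9.2.1 | SAP Table 6(vi) |
|---|---|---|
| IV stop missing because of discontinuation | termination | 23:59 on discontinuation date (same day) |
| IV stops recorded | termination | latest C3 to C6 time |
| No IV record from noon | termination | 0 h |

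Only the last two rows differ. Illustration (assumed dates): randomised 20:00 on day 0, last IV stop 20:00 on day 4, discharged 12:00 on day 5, last contact 12:00 on day 40. Protocol with Day 35 as termination: 40 × 24 − 8 = 952 h. SAP: 4 × 24 + 8 = 104 h.

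**4. The plan's own figure.** Medians of 106 and 156 h give HR = 106/156 = 0.6795 and ln HR = −0.386417, as in SAP 10.4. Schoenfeld's formula gives 4 × (1.960 + 1.2816)² / 0.386417² = 281.5, so 282 events, with power 90.05%. 282/0.94 = 300 subjects. The plan's figure is reproduced.

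**5. Size under each rule.** The documents give no untreated rate, so 3, 6, 9 and 15 of 300 are assumed (1%, 2%, 3%, 5%). Simulation: 150 per arm, exponential times, unstratified two-sided log-rank at 0.05, all treated subjects reach the event, untreated subjects follow the placebo distribution and are split at random between arms, 6,000 runs per cell (Monte Carlo error about 0.4 to 0.6 points). Power with none untreated is 91%.

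| Censoring of untreated subjects | 3 | 6 | 9 | 15 |
|---|---|---|---|---|
| SAP, last IV stop | 90% | 90% | 87% | 85% |
| SAP, 0 h | 91% | 91% | 91% | 89% |
| Protocol, all leave within 24 h | 91% | 91% | 90% | 90% |
| Protocol, half leave within 24 h, half to Day 35 | 87% | 84% | 80% | 73% |
| Protocol, all to Day 35 | 84% | 78% | 72% | 61% |

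The 0 h row is close to simply losing those events: Schoenfeld power is 91.5% with 297 events and 90.1% with 282.

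**6. Direction.** With the split fixed (rivipansel + placebo untreated; 4,000 runs; last IV stop placed near the time the subject would have been ready):

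| Split | Protocol to Day 35 | SAP, last IV stop | SAP, 0 h |
|---|---|---|---|
| 2 + 2 | 84% | 90% | 92% |
| 6 + 2 | 40% | 82% | 91% |
| 2 + 6 | 97% | 94% | 91% |
| 9 + 9 | 61% | 85% | 90% |

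Read to Day 35, the protocol sentence would not simply dilute the effect; it could move the result either way.

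**7. The meaning of termination.** The preceding sentence of the same 9.2.1 item is about leaving the study prematurely. Protocol 6.4.3 separates the Day 35 visit from early termination, and 6.6 defines discontinuation as ceasing before the protocol is completed. A subject who reaches Day 35 has completed. On that reading the protocol sentence is silent about completers, and only Table 6(vi) supplies a time for them.

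**The case for a change.** The best case for acting is that 9.2.1 does more than leave detail to the SAP: it states a specific and different rule for the primary endpoint. A handful of subjects can matter, as the 6 + 2 and 2 + 6 rows show, and two written rules could feed a dispute after unblinding. The edit is one sentence.

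Some of this stands. The mismatch is real, the sentence is in the wrong list, and the sensitivity under the Day 35 reading is large. What does not stand is that the choice of rule is open. The protocol names the SAP as the place for censoring rules, and SAP section 1 records that the team was still blinded when the current version was written, so the governing rule was fixed without sight of treatment effects.

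Nor would the edit improve the analysis. Table 6(vi) has limits of its own. Censoring at the last IV stop falls close to the likely event time and so is informative. Row (ii), on a stop missing without discontinuation, is worded for treated subjects only; an analyst would naturally extend it. Copying the rule into the protocol addresses neither.

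Much of the useful reporting is already planned. SAP 5.5 puts randomised-but-untreated subjects in the subject evaluation table, SAP 8.1.1 reports censoring counts and types by arm, and SAP 5.2 repeats the primary endpoint in a per-protocol set that excludes them.

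**Conclusion.** No change is called for. Protocol 9.2.1 carries a loosely worded, misplaced sentence that differs from SAP Table 6(vi) for untreated subjects with recorded IV stops or with no IV record from noon. The protocol's own referral makes Table 6(vi) the operative rule, and the noon start is a disclosed imputation.

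Under that rule, with 1% to 5% untreated and a random split, power is 90% to 85% (last IV stop) or 91% to 89% (0 h), against 91% with none untreated. The fall to between 84% and 61% is a hypothetical worst case needing two departures together: setting the SAP aside, and treating completion of Day 35 as termination. Aligning the protocol text would leave the SAP rule, the data and the primary result as they are.

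This rests on the planning medians, exponential times, an assumed untreated rate, and the inferred 0 h value in Table 6(vi).

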9.2.2. Analysis of Key Secondary Endpoints

Time to discharge from the hospital and time to discontinuation of IV opioids will be analyzed in the same way as the primary endpoint.

Cumulative IV opioid consumption from the time of the loading dose of study drug to discharge, standardized using morphine equivalents, is expected to be non-normal and heteroscedastic. Therefore it will be analyzed using an analysis of covariance (ANCOVA) model on the ranks of the observed data with treatment, age group (Cohort 1 and Cohort 2 combined or Cohort 1 only), and genotype group as factors. Descriptive statistics summaries will also be presented for raw data.

A fixed-sequence approach will be used to control overall type I error for multiple endpoints (1 primary and 3 key secondary endpoints) based on the Cohort 1 and Cohort 2 combined population. This implies that a given endpoint only achieves significance if the prior endpoint in the sequence is statistically significant. The order for testing against placebo is as follows:

1. Time to readiness-for-discharge;
2. Time to discharge;
3. Cumulative IV opioid consumption from the time of the loading dose of study drug to discharge, standardized using morphine equivalents;
4. Time to discontinuation of IV opioids.

9.2.4. Analysis of Other Secondary Endpoints

Cumulative IV opioid consumption within the first 24 hours post-loading dose of study drug, standardized using morphine equivalents, will be analyzed in the same way as cumulative IV opioid consumption from the start time of the loading dose of study drug to discharge.

Percent of subjects re-hospitalized for VOC within 3 days of discharge will be analyzed using exact methods.

Term	Percentage
GMOs	~75%
Organic	~95%
Natural	~90%
Artificial	~65%
Organic	~95%
Natural	~90%
Artificial	~65%
Organic	~95%
Natural	~90%
Artificial	~65%
Organic	~95%
Natural	~90%
Artificial	~65%

9.4. Safety Analysis

The safety data (eg, AEs, SAEs, physical exams, laboratory tests, vital signs) will be summarized in accordance with the Clinical Data Interchange Standards Consortium (CDISC) and Pfizer Standards (CaPS). Safety data that will be specifically summarized include:

- Adverse events according to CaPS;
- Safety laboratory tests according to CaPS;
- Physical exams and vital signs assessments according to CaPS;
- Incidence of adjudicated ACS and incidence of adjudicated severe and/or generalized cutaneous manifestations analyzed using exact methods.
- Percent of subjects re-hospitalized for VOC within 7, 14 and 30 days of discharge analyzed using exact methods.

The safety analysis set will be all subjects who receive at least one infusion of study drug.

9.5. Interim Analysis

An E-DMC will review unblinded safety data on a regular basis. In addition, the study was designed to have a possible interim futility analysis for Cohort 1 after 150 subjects in Cohort 1 had completed the study. No interim analysis was planned for Cohort 2. The conditional power would have been used for the futility decision-making to maintain the overall nominal significance level for the final efficacy analysis at 0.05 (2-sided test).

If an interim analysis for futility were conducted, the details of the objectives, decision criteria and method of maintaining the study blind as per Pfizer's SOPs would have been documented and approved in an E-DMC charter and the detailed analysis plan documented and approved in a SAP.

9.6. Data Monitoring Committee

This study will use an External Data Monitoring Committee (E-DMC). The E-DMC will be responsible for ongoing monitoring of safety of subjects in the study according to the Charter. The E-DMC will include members, external to the Sponsor, with expertise in the clinical management of adult and pediatric SCD patients, statistics, or clinical pharmacology. The E-DMC will receive safety summaries and subject listings presented by masked treatment groups but will have the option to review fully unblinded safety data and/or efficacy data if necessary.

The E-DMC will review accumulating data from this study on a regular basis, at least every 6 months and particular focus will be placed upon evaluation of the pediatric safety data. The initial data review meeting will occur after the first 6 pediatric subjects (6-11 years of age) have completed the study, or approximately 6 months after first subject first visit (FSFV), whichever comes first. An additional review of subjects 6-11 years of age will occur after 12 of these subjects have completed the study. The sponsor and the E-DMC can

request additional data reviews as they see fit and ad hoc meetings will be arranged to accommodate these reviews. During meetings, the E-DMC will review safety data as defined above.

[REDACTED]

Based on these reviews, the E-DMC will have the capacity to make recommendations to the Sponsor that might impact the future conduct of the study. These may include amending safety monitoring procedures, modifying the protocol or consent, modifying the dosing of the pediatric subjects (6-11 years of age), terminating the study, or continuing the study as designed. The recommendations made by the E-DMC to alter the conduct of the study will be forwarded to Pfizer for final decision. Pfizer will forward such decisions, which may include summaries of aggregate analyses of endpoint events and of safety data which are not endpoints, to regulatory authorities, as appropriate.

In addition to the ongoing review of the safety data in general, the E-DMC will participate in the interim analysis, if performed, to assess futility.

The details around the conduct and responsibilities and roles of the E-DMC will be provided in the E-DMC Charter.

9.7. Safety Endpoint Adjudication Committees

9.7.1. Acute Chest Syndrome Safety Endpoint Adjudication Committee

To help assess the safety endpoint of ACS events in this and the open-label extension study (B5201003), an Acute Chest Syndrome Safety Endpoint Adjudication Committee (ACS-SEAC), consisting of external clinical experts in the relevant clinical areas, will be set up to harmonize and standardize endpoint assessment. The frequency of committee meetings will be dependent on the volume of cases, urgency of review for specific cases, and the preferences of the committee members and the needs of the Sponsor. In order to allow for an unbiased endpoint assessment, members of this committee will be blinded to treatment assignment. The committee will use a-priori defined criteria in tandem with expert clinical judgment to adjudicate the events. Further information about the ACS-SEAC can be found in the respective charter, including a specific description of the scope of responsibilities, a plan where communication timelines are defined, and the exact process and definitions used by the committee to adjudicate the safety events.

